2.0 STUDY RATIONALE

The Radiofrequency ablation procedure offers women a new approach to fibroid treatment that improves bothersome symptoms with the potential for significantly less morbidity compared with current fibroid surgery. The existing studies of Radiofrequency ablation are all uncontrolled trials that demonstrate subjective and objective improvement in fibroid-related symptoms. However, no trials have been conducted to examine the benefit of Radiofrequency ablation in comparison with other surgical fibroid treatments. Our ultimate goal is to conduct a multi-centered, randomized, noninferiority trial of Radiofrequency ablation versus myomectomy (laparoscopic or abdominal) among women with symptomatic fibroids. This trial will provide gold standard evidence to determine if Radiofrequency ablation results in similar symptom improvement as myomectomy but offers the advantages of less operative morbidity and lower rates of re-operation for recurrent fibroid symptoms.

To prepare for a future multi-centered comparative trial of Radiofrequency ablation, we will first conduct an uncontrolled pilot study (the ULTRA study). The pilot will allow us to assess the feasibility of recruiting and retaining study participants to this surgical trial, and establish effective communication and organizational tools among the five study sites. We will also complete essential preparatory work for a future randomized trial; we will create and test study forms, a manual of operations, and a study database that can be easily adapted for a

comparative trial. The ULTRA pilot study will lay the foundation for a successful future comparative study of Radiofrequency ablation.

The ULTRA study will also provide preliminary data on the efficacy of Radiofrequency ablation in a “post-market” setting. This is the first Radiofrequency ablation trial after FDA approval in November 2012. Previous studies have enrolled a highly symptomatic patient population with a minimum menstrual blood loss of 200cc (normal is <80cc) to adhere to the requirements for FDA approval. However, in clinical practice, surgical treatment is offered to women with more moderate fibroid symptoms and we will enroll these patients in the ULTRA study. We will use ULTRA outcome data to estimate effect sizes and standard deviations to calculate an appropriate sample size for a future randomized trial.

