3.0 STUDY OVERVIEW

The ULTRA study is a single-arm trial of 100 premenopausal women with symptomatic uterine fibroids who undergo treatment with the Radiofrequency ablation device. We will evaluate changes in fibroid-related symptoms from pre-treatment values to 3, 6, 12, 18, 24, 30, and 36 months after Radiofrequency ablation. We will also assess operative outcomes including procedure duration, complications, blood loss, post-operative pain, and return to usual activities. We will determine long-term efficacy of Radiofrequency ablation by evaluating the rate of re-treatment for symptomatic fibroids after the Radiofrequency ablation procedure.

Study participants will be recruited at 5 sites within the UC Fibroid Network: UC Davis, UC Irvine, UC Los Angeles, UC San Diego, and UC San Francisco. UC San Francisco will serve as the Coordinating Center for the trial with oversight of all scientific and administrative aspects of the study. All study data will be stored securely in a HIPAA compliant, secure database monitored by the UC San Francisco Coordinating Center. A data safety and monitoring board will oversee participant safety and protection.

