4.0 STUDY OBJECTIVES

The ULTRA study will collect essential preliminary data to guide and inform a future multi-centered, randomized trial of Radiofrequency ablation versus myomectomy. The 2 primary study goals are:

1. To create and implement study protocols, measurements and procedures that will serve as a template for future comparative trials of Radiofrequency ablation.

We will evaluate the efficiency and timeliness of study recruitment. We will create a database and study forms with fibroid specific questionnaires, develop communications and study operations for the coordinating center and each study site, and assess the demand and interest for Radiofrequency ablation among symptomatic women.

2. To collect preliminary data on the changes in fibroid-related symptoms from baseline to 3 years after the Radiofrequency ablation procedure among women with symptomatic fibroids.

We will assess fibroid-related symptoms prior to Radiofrequency ablation treatment and every 6 months for 3 years after surgery. We will evaluate changes in both bleeding and bulk symptoms using validated questionnaires.

Secondary study objectives are as follows:

1. To determine the rate of re-intervention for recurrent fibroid symptoms following the Radiofrequency ablation procedure.
Study participants will be queried every 6 months about recurrent fibroid symptoms and interventions including medical management, myomectomy, uterine artery embolization, MR Guided Focused Ultrasound, or hysterectomy.
2. To evaluate short-term operative morbidity among women undergoing the Radiofrequency ablation procedure.

We will evaluate operative and perioperative morbidity including procedure duration, blood loss, complications, as well as post-operative pain and time to return of usual activities.

3. To evaluate gynecologists' performance during the "learning curve" of introducing the Radiofrequency ablation procedure into practice.

Gynecologists will be asked to rate the difficulty of the Radiofrequency ablation procedure and their confidence with the procedure among the first 10 study participants.

4. To examine the rate of pregnancy and pregnancy outcomes among women who desire future fertility following the Radiofrequency ablation procedure.

We will query study participants at baseline regarding the desires for future fertility and every 6 months after the Radiofrequency ablation procedure. We will ask participants to report any pregnancies and the outcome of those pregnancies.

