8.0 MEASURED VARIABLES

8.1. Outcome Variables

Outcomes will be measured at baseline prior to the Radiofrequency ablation procedure and at multiple time points for 3 years after the Radiofrequency ablation procedure. Questionnaires will be administered to evaluate patient-reported fibroid symptoms, operative outcomes, adverse events, the rate of re-intervention for fibroid symptoms, and surgeon self-assessment of skill and satisfaction. In the following section, outcome measurements are described in detail.

8.1.A Questionnaires to Assess Symptoms

These are validated questionnaires to assess the change in symptoms over time following the Radiofrequency ablation procedure.

1. **Uterine Fibroid Symptom-Quality of Life (UFS-QOL):** The UFS-QOL is a standardized questionnaire to evaluate fibroid-specific symptoms including heavy bleeding and urinary and bowel symptoms as well as the impact of fibroid symptoms on quality of life.^{4,5} The UFS-QOL has been used widely in studies of uterine preserving fibroid treatments including trials of Uterine Artery Embolization and MR Guided Focused Ultrasound.
2. **SF-36:** The SF-36 is a widely used, validated questionnaire to assess overall quality of health.⁶ There are 2 primary domains: Mental Health and Physical Health. The SF-36 has been used in multiple studies of women's health for a wide range of conditions including heavy uterine bleeding and symptomatic fibroids.
3. **Menstrual Impact Questionnaire (MIQ):** The MIQ is a validated questionnaire to evaluate the impact of heavy menstrual bleeding on quality-of-life.⁷ The MIQ has been used in trials of heavy bleeding that includes women with uterine fibroids.
4. **Overall Treatment Effect:** The Overall Treatment Effect used for this study is modified from a validated questionnaire to determine changes in symptoms following a medical intervention.⁸ The OTE consists of three questions that query women about whether symptoms have improved or not since treatment. These questionnaires have been compared with measures from the UFS-QOL among gynecologic patients.⁹ Three additional questions are generally linked to the OTE to assess overall patient satisfaction with treatment. This 6 question adapted OTE has been used in prior studies of women undergoing the Radiofrequency ablation procedure.

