12.0 STATISTICAL CONSIDERATIONS

The primary analyses will evaluate changes from baseline to 1, 3, 6, 12, 18, 24, 30, and 36 months after Radiofrequency ablation treatment in all patient-reported outcomes including scores for the UFS-QOL and other standardized symptom and quality of life questionnaires. We will use ANOVA to evaluate the overall differences among these multiple time points in change scores, adjusting for potential confounding factors and baseline values to increase power. We will test the normality assumption and use nonparametric alternative models if the normality assumption is violated. We will use paired t-tests to directly compare mean scores from baseline to all follow-up time points.

Additional Planned Analyses: Descriptive analysis of the following outcomes will be reported with proportions and standard deviations for categorical outcomes and means with standard deviations for continuous outcomes.

1. Operative Outcomes: We will report intraoperative and immediate and long-term postoperative outcomes as described in Section 8.1.B.
2. Treatment Failure: Treatment failure is defined as any additional treatment for fibroids after the Radiofrequency ablation procedure including medical management for fibroid-related symptoms, myomectomy, hysterectomy, uterine artery embolization, MR Guided Focused Ultrasound, endometrial ablation, dilation and curettage, or any new and emerging fibroid treatments.

3. Resource Utilization: Medical resource utilization is measured by the number of hospitalizations, unplanned physician or clinic visits, and missed days of work or usual activities due to Radiofrequency ablation treatment.
4. Pregnancy Outcomes: We will report the proportion of women who become pregnant following Radiofrequency ablation treatment among all study participants and among the subgroup of women who report that they are actively trying to become pregnant prior to undergoing Radiofrequency ablation. For women who do become pregnant during the study, we will report the proportion who undergo miscarriage, abortion, or live births. We will also report obstetrical and perinatal complications.

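### Three-year treatment failure is to be reported as a proportion with a standard deviation, which shows no precision, and neither the denominator nor the handling of incomplete follow-up is stated

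*Combined protocol and SAP*

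**What the plan says.** Under the additional planned analyses, Section 12.0 sends several outcomes to descriptive summary, "reported with proportions and standard deviations for categorical outcomes and means with standard deviations for continuous outcomes". Treatment failure is item 2 of that list: "Treatment failure is defined as any additional treatment for fibroids after the Radiofrequency ablation procedure", with examples that run from medication to hysterectomy. The section gives no time point, denominator, rule for women who stop responding, or confidence interval for it. Item 4, on pregnancy, does name its denominators.

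The outcome has a prominent role. Section 3.0 states: "We will determine long-term efficacy of Radiofrequency ablation by evaluating the rate of re-treatment for symptomatic fibroids". Section 4.0 has as its first secondary objective: "To determine the rate of re-intervention for recurrent fibroid symptoms following the Radiofrequency ablation procedure". On ascertainment, Section 4.0 adds: "Study participants will be queried every 6 months about recurrent fibroid symptoms and interventions including medical management". Section 8.1.D has all data after the six-week visit collected by mail, online or by telephone, up to 36 months. Section 10.0 asks the data and safety monitoring board to review dropout, but no dropout rate is projected anywhere.

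**The concern.** There are two separate faults.

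The first is a stated rule that is wrong. A standard deviation attached to a proportion looks like an error bar but is not one. It carries no information beyond the proportion itself, and it vanishes when no events are seen, which is when a reader most needs an upper limit.

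The second is an omission. Failures accrue over three years and are learned of mainly from remote self-report, so some women will have incomplete histories. A simple proportion has no natural way to use a woman who was followed for 18 months without failing and then stopped answering. Depending on how she is counted, the same data give different failure rates.

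At stake is the figure the protocol names as its evidence on long-term efficacy. It could be published without a usable measure of uncertainty, and with a value that depends on a choice made after the data are seen.

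**Working it through.** **The plan's own figures.** The documents give no expected failure rate, precision or power for treatment failure. The only power figure is the 7.2-point detectable change in UFS-QOL (Section 12.0, SD 21.7, n = 100, 90% power). It reproduces closely (21.7 × (1.960 + 1.282)/10 = 7.03) and does not bear on this point.

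**Inputs.** From the documents: n = 100 (Section 3.0) and follow-up of 36 months (Section 8.1). Assumed: true 36-month failure F = 15%; loss L = 5% to 30% over 36 months; constant hazards; loss unrelated to failure.

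**Step 1, the standard deviation.** For a binary outcome SD = sqrt(p(1-p)), while the standard error is SD/sqrt(n). The exact limits are Clopper-Pearson.

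| Failures in 100 | SD (points) | Exact 95% interval |
|---|---|---|
| 0 | 0 | 0 to 3.6% |
| 1 | 9.9 | 0.03% to 5.4% |
| 10 | 30 | 4.9% to 17.6% |
| 20 | 40 | 12.7% to 29.2% |

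At 20 in 100, p ± SD runs from -20% to 60%. The standard error there is 40/sqrt(100) = 4 points. Doubling the sample would leave the SD at 40.

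**Step 2, loss to follow-up.** Take 36 months as the unit of time. Then h = -ln(1-F) = 0.1625 and l = -ln(1-L). The share neither failed nor lost by 36 months is S = (1-F)(1-L). The share observed to fail is C = h/(h+l) × (1-S).

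- All treated women as denominator, lost women counted as non-failures: C.
- Only women with known status (seen to fail, or followed to 36 months): C/(C+S).

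At L = 20%: l = 0.2231, S = 0.85 × 0.80 = 0.680, and C = (0.1625/0.3857) × 0.320 = 0.13485. The known-status figure is 0.13485/0.81485 = 0.16549.

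| Loss | S | All 100 as denominator | Known status only |
|---|---|---|---|
| 5% | 0.8075 | 14.6% | 15.3% |
| 10% | 0.765 | 14.3% | 15.7% |
| 20% | 0.680 | 13.5% | 16.5% |
| 30% | 0.595 | 12.7% | 17.6% |

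The truth in every row is 15%. At 30% loss the two readings differ by 17.6 - 12.7 = 4.9 points. With a true failure of 10% the pair at 30% loss is 8.4% and 11.8%; with 20% it is 16.9% and 23.2%. A third reading, women who respond at 36 months with a complete history, is unbiased when loss is unrelated to failure.

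**Step 3, the alternative.** In 1,500 simulated trials of 100 women per scenario on the protocol's visit schedule (true failure 10%, 20% and 30%; loss 5% to 30%), the Kaplan-Meier estimate averaged within 0.4 points of the truth. Its 95% intervals covered the truth in 92% to 95% of trials.

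**The case against.** This is a descriptive secondary outcome in a single-arm pilot. A reader given p and n can work out a binomial interval unaided. The distortion is modest: at 15% true failure and 20% to 30% loss, counting lost women as non-failures costs 1.5 to 2.3 points, less than one standard error (sqrt(0.15 × 0.85/100) = 3.6 points), and at low loss it is negligible. Section 2.0 frames the future trial as noninferiority on symptom improvement, with ULTRA supplying effect sizes and standard deviations, so it would go too far to say the next trial cannot be planned.

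Much of that stands, and it limits the weight of the point. It does not rescue the standard deviation as a summary of a proportion, and an interval worked out from p and n would still ignore incomplete follow-up. Low counts are also plausible: Section 1.0 reports one re-intervention among the 135 women of the pivotal trial, although the definition here is broader and the follow-up longer.

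Three stronger readings are tempting, and the documents do not support them:

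- *The plan understates failure and so favors the device.* No denominator is stated, and the direction reverses if only women with known status are counted. If loss depends on failure, the direction is unknown.
- *Pooling medication with surgery is an error*, because Section 2.0 hopes the device "offers the advantages of less operative morbidity and lower rates of re-operation for recurrent fibroid symptoms". The objective in Section 4.0 expressly includes medical management, so the definition matches its objective.
- *Means are wrong for perioperative measures.* Section 1.0 quotes a median for blood loss but an average for return to activities, so a planned mean for the latter matches the cited comparator.

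**Conclusion.** The point holds in two parts. The rule pairing proportions with standard deviations is wrong as written; this needs no assumption, and it affects every categorical outcome in that list. For treatment failure, the plan also leaves open the denominator and the treatment of women lost to follow-up. The resulting error can go either way: under the assumptions above, from about 2.3 points too low to 2.6 points too high at 30% loss, and under 1 point in either direction at 10% loss or less. The failure rate, the loss rates, the constant hazards and the independence of loss from failure are all assumptions; the documents give none of them for this trial. The correction should be made, but the point does not touch the primary symptom analyses.

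**What to change.** In Section 12.0:

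1. Replace standard deviations of proportions with exact 95% confidence intervals, and state the denominator for each proportion.
2. Report treatment failure as Kaplan-Meier (or interval-censored) cumulative incidence at 12, 24 and 36 months, timed from the date of ablation and censored at the last completed questionnaire, with 95% confidence intervals and numbers at risk.
3. Add a sensitivity analysis for women lost to follow-up, because Kaplan-Meier also assumes that loss is unrelated to failure. For example, show the 36-month figure with lost women assumed to fail at a range of higher and lower rates than those who stayed.

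The cost is a change of wording, collection of the date of any re-treatment, and a little more analysis. Reporting procedural re-intervention separately from medical management, and medians for skewed perioperative measures, are optional suggestions rather than corrections.

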7.4 Procedure Training and Support

Study investigators will be trained to perform the Radiofrequency ablation procedure during a one day in-service conducted by Halt Medical. The training includes didactic sessions and hands-on simulation of laparoscopic ultrasound and use of the Radiofrequency Probe. A trained Radiofrequency ablation physician employed by Halt Medical will be present in the operating room to provide technical support during the first 5 cases each investigator performs. This Radiofrequency ablation trainer can be present for additional cases at the request of the investigator as needed for additional support.

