7.5 Use of Radiofrequency ablation Outside of The ULTRA Study

The procurement of Radiofrequency ablation to the UC Operating Rooms is through the UC policies and procedures for IRB approved clinical trials, not through the pathway for device use in general clinical practice. Therefore, there will be no use of Radiofrequency ablation at study sites outside of participants enrolled in ULTRA/ULTRA Registry. Study investigators will not use Radiofrequency ablation for patients undergoing procedures who are not enrolled in ULTRA/ULTRA Registry. Among study participants, investigators will only use Radiofrequency ablation according to the ULTRA protocol.

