Sample Size Calculation: The sample size of 100 was selected to allow each site investigator to perform an adequate number of cases to become competent and comfortable with the Radiofrequency ablation Procedure in anticipation of conducting future comparative trials. Each investigator (n=10) will perform 10 procedures, the first 5 cases with Halt support staff in the operating room and the remaining 5 cases independently. After 10 cases, the investigator will have the appropriate expertise to conduct a comparative trial of Radiofrequency ablation without requiring a "run-in" period of training cases.

The sample size of 100 will also provide sufficient power to evaluate the efficacy of Radiofrequency ablation as measured by changes in the UFS-QOL score from baseline to 3, 6, 12, 24, and 36 months following the procedure. Prior studies of women who undergo Radiofrequency ablation have shown the standard deviation of the UFS-QOL to be 21.7. Assuming 5% type 1 error and 90% power, we will be able to detect a minimal change of 7.2 in the UFS-QOL. This is a clinically significant change because meaningful improvements in quality of life are generally felt to occur with a minimum 10 point change in the UFS-QOL from baseline.

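### The learning-curve objective has no analysis by case order or manufacturer support, and the UFS-QOL tests and power figure make no allowance for 10 surgeons with 10 cases each

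*Combined protocol and SAP*

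**What the plan says.** The Sample Size Calculation in Section 12.0 gives two grounds for 100 women. The first is training: "The sample size of 100 was selected to allow each site investigator to perform an adequate number of cases to become competent". The structure is explicit: "Each investigator (n=10) will perform 10 procedures, the first 5 cases with Halt support staff in the operating room", and "the remaining 5 cases independently". The section then states that a surgeon with 10 cases will be ready for a comparative trial without a training period. The second ground is power: with an SD of 21.7, 5% type 1 error and 90% power, the detectable UFS-QOL change is 7.2 points, and 10 points is called meaningful.

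Secondary objective 3 in Section 4.0 is the learning curve over the first 10 participants: "Gynecologists will be asked to rate the difficulty of the Radiofrequency ablation procedure and their confidence with the procedure". The only related item among the additional analyses in Section 12.0 is: "We will report intraoperative and immediate and long-term postoperative outcomes as described in Section 8.1.B". These are summarised as means, proportions and standard deviations. Table 1 in Section 8.1.B lists the gynecologist's difficulty rating but no confidence rating.

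The primary analyses are an ANOVA of change scores, adjusted for baseline and unnamed confounders, and paired t-tests from baseline. Section 8.2 gives its additional measurements, among them the surgeon characteristics of 8.2.B, a role as confounders when symptom change is modelled.

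Section 7.4 puts a manufacturer physician in the operating room for each investigator's first 5 cases and adds that this trainer "can be present for additional cases at the request of the investigator as needed for additional support". Section 2.0 states the use of the results: "We will use ULTRA outcome data to estimate effect sizes and standard deviations to calculate an appropriate sample size for a future randomized trial".

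**The concern.** A summary over all cases cannot show a curve. Objective 3 asks how performance changes over a surgeon's first 10 cases, so it needs results ordered by case number. None are planned, and no line of Section 12.0 covers the confidence rating. The claim that surgeons are ready after 10 cases is the main reason for the sample size, and the plan does not say how the data will be looked at to support it.

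Half of the planned cases (50 of 100) are operated on with manufacturer staff present. Pooled procedure time, blood loss and complications therefore mix two operating conditions, and the next trial is meant to use surgeons who have finished training.

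Women treated by the same surgeon may have correlated outcomes. If they do, and if the results are meant to apply beyond these 10 surgeons, paired t-tests on 100 women give standard errors that are too small, and the 7.2-point figure is optimistic. ULTRA is meant to supply planning figures for a multi-centre trial, so that wider reading is the relevant one.

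**Working it through.** **Inputs from Section 12.0.** n = 100; 10 surgeons with 10 cases each; SD 21.7; 5% type 1 error; 90% power; threshold 10 points. **Assumptions.** Two-sided test (sidedness is not stated; a one-sided test gives 6.35 to 6.39 and does not match). 21.7 is the SD of the change. All 100 women are analysed. The surgeon ICC of the change score is not given, so a range is shown.

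**1. The plan's own figure.**
- Normal: 21.7 × (1.960 + 1.282) / √100 = 7.03.
- Noncentral t, 99 df: 7.10.
- Power for 7.2 at n = 100: 0.913 (normal) or 0.908 (t).

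The stated 7.2 is what an independence calculation gives, to within about 0.1 to 0.2 points.

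**2. Allowing for surgeon.** Design effect DE = 1 + (10 − 1) × ICC. Effective n = 100/DE. The correct standard error is √DE times the naive one, so the naive one is too small by 1 − 1/√DE. Detectable change is 7.03 × √DE (normal), or from a noncentral t with 10 − 1 = 9 df.

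| Assumed ICC | DE | Effective n | Correct SE / naive SE | Naive SE too small by | Detectable change, normal | Detectable change, 9 df |
|---|---|---|---|---|---|---|
| 0 | 1.00 | 100 | 1.00 | 0% | 7.0 | 7.9 |
| 0.01 | 1.09 | 92 | 1.04 | 4% | 7.3 | 8.3 |
| 0.05 | 1.45 | 69 | 1.20 | 17% | 8.5 | 9.5 |
| 0.10 | 1.90 | 53 | 1.38 | 27% | 9.7 | 10.9 |

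The detectable change reaches 10 points at an ICC of ((10/7.034)² − 1)/9 = 0.11 (normal), or about 0.066 with 9 df.

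**3. Effect of pooling the two halves on planning figures.** If mean UFS-QOL change differed by d between cases 1–5 and 6–10, the pooled mean would lie d/2 from the later-case mean, and the pooled SD would be √(21.7² + d²/4). For d = 10 the mean moves 5 points, but the SD moves only from 21.7 to 22.3.

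**4. What a split can show.** Comparing 50 with 50, ignoring surgeon effects, the detectable difference is 21.7 × (1.960 + 0.842) × √(2/50) = 12.2 at 80% power and 21.7 × (1.960 + 1.282) × √(2/50) = 14.1 at 90%. Power for a 10-point difference is 63%. For cases 6–10 alone, the 95% interval for mean change has half-width 6.2 points, against 4.3 for all 100.

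**5. Is the split at case 5 clean?** Section 12.0 describes the last five cases as performed independently. Section 7.4 lets the trainer attend further cases on request. Case number alone may therefore misclassify support.

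**The case against.** The strongest reply is that this is an uncontrolled pilot, that surgeon is not absent from the plan, and that the loss of precision is hypothetical. Much of this stands, and it rules out several stronger readings.

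- *The plan ignores surgeon.* A reader might infer this, but Section 8.2.B collects training, surgical volume and laparoscopic experience, and Section 8.2 allows them as confounders. What is missing is surgeon identity, case number and support. Baseline traits supply none of these, cannot enter a paired t-test, and are assigned only to the symptom analysis.
- *Objective 3 has no reporting at all.* The difficulty rating is in Table 1 and so falls under the descriptive report. The gap is the lack of ordering by case and of any stated report of confidence.
- *Precision is overstated throughout.* Operative outcomes are purely descriptive, with no planned standard errors or tests. The point applies only to the patient-reported outcome tests and the 7.2 figure. Even there it needs a positive ICC and inference beyond these 10 surgeons; if inference is confined to them, the inflation does not apply.
- *The next trial should be planned from cases 6–10 alone.* The documents do not support this. Section 12.0 envisages surgeons past 10 cases, so cases 6–10 are still within the stated training period. Pooling barely moves the SD, and halving n makes it less certain.
- *Registry cases distort case order.* Section 7.5 mentions the Registry ("no use of Radiofrequency ablation at study sites outside of participants enrolled in ULTRA/ULTRA Registry") but says nothing on whether such cases come before or between a surgeon's ULTRA cases.

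The claim of readiness after 10 cases is also a justification of sample size, not a stated hypothesis. It still makes a view of the data by case order worth having.

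**Conclusion.** The point holds as a moderate gap. As written, Section 12.0 cannot show the learning curve of secondary objective 3, and its UFS-QOL tests and power statement do not reflect the 10-by-10 surgeon structure.

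The size of the clustering effect is conditional. The power figure hardly changes at an ICC of 0.01 under the normal calculation (7.3). At 0.05 the detectable change stays below the plan's 10-point threshold by either method. At 0.10 it is 9.7 or 10.9, so it passes the threshold only when the small number of surgeons is counted. These results assume equal numbers per surgeon, 21.7 as the SD of change, and inference beyond the 10 surgeons.

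For planning the next trial, pooling threatens the mean effect more than the SD, and only if outcomes differ between early and later cases, which the documents do not establish.

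**What to change.** 1. Record surgeon, case number and actual trainer attendance for every case. Reconcile Section 7.4 with the Sample Size Calculation on whether cases 6–10 are independent.
2. In Section 12.0, add a report for objective 3: difficulty, confidence, procedure time, blood loss and complications, by case order within surgeon and by actual support. Label any comparison of periods exploratory, since 50 against 50 detects only about 12 to 14 UFS-QOL points.
3. Add a sensitivity analysis of UFS-QOL change with a surgeon random intercept, or cluster-robust standard errors with a small-sample correction for 10 surgeons, and report the ICC.
4. When planning the randomized trial, show the UFS-QOL effect and SD for cases 6–10 beside the pooled figures, not in place of them.

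**Cost.** Mainly SAP wording, with no extra participants. Table 1 lists neither case number nor trainer attendance, so a form field may have to be added. Intervals will be somewhat wider, and support and experience cannot be separated because they change together.
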